4.4 FISS FALLS DIARY

All study participants will be given a Falls Diary, for their personal use, which will be posted to them by the central research team following randomisation. The Falls Diary will contain a definition of a fall. Participants will be asked to record the number of falls they have over each month and record the severity of the fall based on fall outcome in line with the NDNQI definitions (e.g. fall resulted in injury that required surgery would be classed as 'major' or for FISS participant documentation, category D). Participants will be encouraged to use the Falls Diary, but use of the diary is not a requirement of the study. Falls Diaries will not be collected or used as source data.

Reminders (electronic or telephone) to participants to report monthly falls data will be coordinated by the central research team. Participants will have the option to provide falls data by post, online form or telephone. Reminders and follow-up calls may be made for non-responders. Participants will be followed up a maximum of twice each month to ask for falls data.

To ensure accurate data collection, the database will be restricted to allow falls data entry only within a one-year period from the randomisation date. Any falls occurring before or after this period will be prevented from being recorded in the system.

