2.2 PRIMARY OBJECTIVE

To determine the effect of SAF and usual care on the rate of falls in stroke survivors in the 12 months after discharge from hospital, compared to usual care alone.

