5.1.1 Primary Endpoint

The primary outcome is the rate of reported participant falls in the 12 months following randomisation.

Table 2: Primary Endpoint

Objective	Endpoint Measure	Time Point	Method of
			Collection

Page 19 of 53

FISS Protocol Final Version 1.0 date 24-Jul-2025

To determine the	Number	of	falls	Randomisation	to	Participant reported
effect of SAF and	reported	by	а	month 12.		by short forms online,
usual care on the rate	participant	t expre	ssed			by phone or by post
of falls in stroke	as a rate.					each month.
survivors in the 12						
months after						
discharge from						
hospital, compared to						
usual care alone.						

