5.8 RECRUITMENT

5.8.1 Expected duration of participant participation

Participants will be involved in the study for 12 months once randomised. Active participation ends once the participant completes the final set of questionnaires and falls reporting at 12 months, or as soon as possible thereafter.

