6.1.1 Baseline

Following consent but prior to randomisation, baseline data will be collected, this will include (but not limited to) demographic and contact details and the following baseline questionnaires:

- Nottingham Extended Activities of Daily Living (NEADL) [14]
- Short Falls Efficacy Scale-International (Short FES-I) [13]
- Patient Health Questionnaire 8 (Participant PHQ-8) [15]
- Modified Barthel Index (MBI)
- Quality of Life (EQ-5D-5L) [16]
- Health Resource Questionnaire
- Patient Health Questionnaire 8 (Carer PHQ-8)*

Baseline data will be collected by research staff or FISS trained stroke healthcare professionals once they are discharged, either in person at the participant's home or over the phone, where possible. Data will be captured directly into REDCap, or where an electronic device is not available, into a paper workbook transcribed into REDCap.

Participants will be randomised using a web-based, concealed randomisation system to receive either the SAF intervention in addition to usual care or usual care alone. The participant

Page 33 of 53

FISS Protocol Final Version 1.0 date 24-Jul-2025

will be told by a member of stroke service which arm of the study they have been randomised to at the time of randomisation (where possible) or as soon after randomisation is completed.

Baseline data collection and randomisation is likely to take place on the same day and will need to be collected within 28 days of discharge as per remote consent. Where this is not possible, randomisation can take place remotely and the participant contacted to inform them of their treatment allocation. This will need to be within 1 or 2 days of collecting the baseline data.

*The Carer PHQ will be posted to the participant's contact address once the participant is randomised. The baseline carer PHQ will be completed by the carer (electronic or post) and returned to the NCTU. Where randomisation is done in person and the carer is available, this can be done at the point of randomisation.

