6.2.1 Monthly Falls Reporting

Follow-up of participants will start one month after randomisation and continue for the duration of their 12-month participation. Participants will be asked to keep a record of any fall they have during their 12-month participation. Participants will be provided with Falls Diary to support recollection of the falls they have had each month. The use of the Falls Diary will be encouraged but not mandated and Falls Diaries will not be considered source data.

Page 34 of 53

FISS Protocol Final Version 1.0 date 24-Jul-2025

Each month, participants will be contacted about any falls they may have had in the previous 30 days. They will be asked up to three questions about their falls; if they have fallen; how many falls they have had and the severity of each of the falls. Monthly falls reporting will be collected electronically, via telephone or via post using paper forms (if required). If a participant has not fallen in the previous 30 days, they will need to complete the monthly falls report as no falls for that reporting period.

Falls severity will be assessed using the National Database of Nursing Quality Indicators (NDNQI) [12] scale. The scale categorises falls into five levels, however for the purpose of the study, only four will be used: none, minor, moderate and major. The fifth level, death, won't be self-reported via questionnaires.

6.2.2 3-and 9-month follow-up questionnaires

Participants will complete a questionnaire pack (online, postal or telephone) 3- and 9-months after randomisation which will include the following:

- Quality of Life (EQ-5D-5L) [16]
- Health Resource Questionnaire

6.2.3 6-and 12-month follow-up questionnaires*

Participants and their carers will complete a questionnaire pack (online, postal or telephone) 6- and 12-months after randomisation which will include the following:

- Nottingham Extended Activities of Daily Living (NEADL) [14]
- Short Falls Efficacy Scale-International (Short FES-I) [13]
- Patient Health Questionnaire (Participant PHQ) [15]
- Quality of Life (EQ-5D-5L) [16]
- Health Resource Questionnaire
- Patient Health Questionnaire (Carer PHQ)
- * Where participants are not able to complete to questionnaires themselves or have a family or friend to support questionnaire completion, additional support may be available from their local stroke service. Availability of this will depend on local service resource and may vary from service to service.

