7.2.2 Sample size and justification

We assume that stroke survivors will have an annual falls rate somewhere between that in community dwelling stroke survivors up to 5 years post stroke in the FAST study (1.8 falls per year) and that of participants in care homes observed in the FinCH study (3.2 falls per year). Using the upper limit of the 95% confidence interval for the overdispersion parameter (FinCH study; 1.1) and assuming an annual falls rate of 2.5 falls per year per participant, 416 evaluable participants would be required to detect a relative difference of 33% in falls rates (i.e. to 1.675 falls per year) using a negative binomial model, with 90% power at the 5% significance level (2-sided) – or 208 per arm. Sample size calculations were performed using PASS 2022 (NCSS).

This difference was deemed a clinically important difference by our FISS PPI group and in the FinCH study. A survey of occupational health professionals showed that 15/27 (58%) would consider adoption of the SAF program if the falls rate was reduced from 3 to 2 falls per year (a 33% reduction), with 3/27 (11.5%) saying they would not consider adoption.

The negative binomial model takes into account exposure, but there is a risk that no robust primary outcome data are collected from some individuals. Therefore, we will inflate the sample size by 10% and aim to randomise 464 participants, or 232 per arm. This sample size also provides 90% power to detect a relative difference of 34% and 36% if the falls rate was lower than expected at 2 and 1.5 falls/year.

The primary outcome event rate is based on the best evidence currently available. However, we recognise that it is an estimate, and our assumptions will be monitored by the DMC throughout the study. They will advise whether a sample size adjustment is necessary.

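### The falls-entry rule, the 30-day look-back and the discharge-based objectives do not line up with an endpoint of 12 months from randomisation

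*Protocol*

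**What the plan says.** **Database restriction.** Protocol section 4.4 says that "the database will be restricted to allow falls data entry only within a one-year period from the randomisation date". The sentence after it bars falls that occurred outside that year. The first sentence is about when data are entered, the second about when the fall happened.

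**Late returns.** Section 5.8.1 ends active participation once the participant completes the final questionnaires and "falls reporting at 12 months, or as soon as possible thereafter". Section 4.4 offers post, online form or telephone, with up to two follow-ups a month. Under section 7.1.2, questionnaires returned to the trials unit are entered by its staff.

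**Content of the monthly report.** Section 6.2.1 says that each month "participants will be contacted about any falls they may have had in the previous 30 days". It lists up to three questions: whether the participant fell, how often, and how severe each fall was. A fall date is not listed. The falls diary in section 4.4 works by month, and is neither collected nor used as source data.

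**Exposure.** Section 7.2.5 counts exposure as the number of months with data.

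**Start of the clock.** The primary objective (section 2.2) concerns the "rate of falls in stroke survivors in the 12 months after discharge from hospital". The primary endpoint (section 5.1.1) is "the rate of reported participant falls in the 12 months following randomisation". Section 6.1.1 says that baseline data "will need to be collected within 28 days of discharge as per remote consent". Randomisation is usually on the same day, otherwise within 1 or 2 days.

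**The concern.** These settings determine which falls reach the primary outcome, and a later analysis plan cannot recover what the form or database never held.

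The month-12 report falls due just as the year closes. If entry stops at one year, a form that is posted, chased or keyed afterwards is refused, and slow responders lose their last month. If the restriction is instead on when the fall occurred, the listed items give no date to apply it to.

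A 30-day look-back does not fill a calendar month, so the days asked about and the months counted as exposure differ.

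The falls objectives also claim early post-discharge time that the endpoint never observes. Table 2 shows both start points in one row.

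At stake are the completeness of the last quarter's falls count, the absolute falls rate, and agreement between the stated objective and what is estimated.

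**Working it through.** **1. Reproduce the plan's sample size, so that any loss of exposure can be priced.**

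Inputs from section 7.2.2: control rate 2.5 ("assuming an annual falls rate of 2.5 falls per year per participant"), intervention rate 1.675 (ratio 0.67), overdispersion 1.1, two-sided 5%, 90% power, 10% loss. Exposure t = 1 year.

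n per arm = [1.960 × √V0 + 1.2816 × √V1]² / (ln 0.67)²

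- V1 = 1/(2.5t) + 1/(1.675t) + 2 × 1.1 = 0.400 + 0.597 + 2.2 = 3.197
- V0 (pooled mean rate 2.0875) = 2/(2.0875t) + 2.2 = 0.958 + 2.2 = 3.158
- n = (3.483 + 2.291)² / 0.1604 = 207.9, so 208 per arm and 416 in total. This matches the plan.
- 208/0.9 = 231.1, so 232 per arm and 464 in total. This also matches.

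**2. Look-back.** Table 6 schedules 12 monthly reports. 12 × 30 = 360 days, so at least 5 of 365 days (1.4%) are not asked about.

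- Control falls not asked about: 2.5 × 5/365 = 0.034 per participant.
- Rate ratio if both arms are short by the same factor: (1.675 × 360/365)/(2.5 × 360/365) = 0.67, unchanged.
- Falls averted at the design rates: 2.5 − 1.675 = 0.825. With 360-day counts treated as a full year: 0.825 × 360/365 = 0.814. Cost per fall averted (section 8.3) would then be too high by a factor of 365/360, or 1.4%.

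**3. Month 12 lost, worst case for everyone.** t = 11/12.

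- Exposure lost: 1/12 = 8.3%. Control falls lost: 2.5/12 = 0.21. One third of the months 10-12 secondary outcome is lost.

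Power = Φ{(|ln 0.67| × √208 − 1.960 × √V0)/√V1}, with V0 and V1 recomputed at each t:

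| Exposure | Power at 208 per arm |
|---|---|
| 1 year | 90.0% |
| 360/365 | 89.9% |
| 11/12 | 89.2% |

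**4. Discharge to randomisation.** At most 28 days, plus 1 to 2 if randomisation is not on the same day. 28/365 = 7.7% and 30/365 = 8.2% of a year. At 2.5 falls per year, 28 days correspond to 2.5 × 28/365 = 0.19 falls.

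**5. The two readings of section 4.4.**

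- Restriction on entry date: a month-12 report keyed after day 365 is refused. This contradicts section 5.8.1 and leaves no time for postal return.
- Restriction on fall date: this agrees with section 5.8.1, but none of the three listed questions yields a date.

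Neither reading works as written.

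**The case against.** The second sentence of the section 4.4 rule speaks of when falls occurred, and section 5.8.1 accepts reporting after 12 months. The more coherent intent is therefore a limit on occurrence, loosely worded. The database specification is not shown, and records could be limited by scheduled reporting month without fall dates. Thirty days may simply stand for a month. Counting from randomisation is consistent across the endpoint, database and follow-up text, and falls before randomisation cannot reflect a treatment effect.

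Much of this stands. It shows that several stronger conclusions a reader might infer are not supported:

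- *That late month-12 forms will be blocked.* This is one of two readings.
- *That the 12-month rate is not delivered, or the rate ratio is biased.* The primary model incorporates exposure (sections 7.2.3 and 7.2.5). A missing month removes its count and its exposure together, and the 30-day shortfall is common to both arms.
- *That late reports overlap or leave gaps.* If the look-back were anchored on completion, a report d days late would miss the first d days of its period and overlap the next by d days. The protocol does not state that anchor.
- *That a missed month can never be recovered.* No catch-up procedure is described, but section 7.2.5 promises every attempt to collect missing data.
- *That a one-month return window applies generally.* Footnote 3 to Table 1 grants it only for the pilot calculation.

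The objection does not remove the conflict between the entry-date wording and section 5.8.1, the absence of a fall date from the listed items, the mismatch between 30 days and a month, or the two start points.

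**Conclusion.** The point holds as a set of inconsistencies in how the primary outcome is captured and described. It does not show that the primary comparison fails.

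Taking the text literally, 1.4% of days are not asked about, and the objectives begin up to about 28 to 30 days before the endpoint. That offset is a maximum, not an expected value, and is a conflict of wording in the objectives. The 89.2% power figure assumes that entry closes at one year and that every participant's month-12 report is then lost, with all other design assumptions of section 7.2.2 holding. The cost in power is therefore under one percentage point.

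The rate ratio would be biased only if late or lost reports differed by arm, which the protocol gives no ground to assume. The understatement of absolute rates and of falls averted assumes that 30-day counts are divided by calendar months.

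It is worth correcting because the change is cheap and reports refused or falls left undated may be hard to recover later.

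**What to change.** - **Section 4.4:** restrict falls records by reporting period, not by entry date. Keep the month-12 form open for a stated late-return window, consistent with section 5.8.1.
- **Section 6.2.1:** put fixed start and end dates on each monthly report, so that the 12 periods cover the year from randomisation without gaps or overlaps however late the form is completed. Individual fall dates are then not needed.
- **Section 7.2.5:** compute exposure from the periods actually covered by returned reports.
- **Synopsis, sections 2.2 and 2.3, and Tables 2 and 3:** restate the primary and falls objectives as 12 months after randomisation.

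The cost is one database setting, revised form text and aligned protocol wording. Sample size and number of participant contacts are unchanged.

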5. STUDY DESIGN

5.1 STUDY CONFIGURATION

FISS is a pragmatic, parallel group, multicentre, randomised controlled trial (RCT) comparing the SAF intervention and usual care to usual care for people discharged home after a stroke, confirmed using either a CT or an MRI scan.

Embedded within the study is a theoretically informed mixed-methods process evaluation study. Qualitative data will be collected during interviews with participants (and dyad interviews with some family members) and their Falls Lead. See section 9 for further details.

A health economic evaluation will be conducted to establish the cost-effectiveness of the SAF intervention in addition to usual care compared to usual care alone. See section 8 for more details.

A study within a trial (SWAT) will be included to determine whether access to an animated video translated into four commonly spoken languages, in addition to the participant information sheet, improves recruitment and retention into the FISS study compared to the participant information sheet alone. See section 10.

5.1.1 Primary Endpoint

The primary outcome is the rate of reported participant falls in the 12 months following randomisation.

Table 2: Primary Endpoint

Objective	Endpoint Measure	Time Point	Method of
			Collection

Page 19 of 53

FISS Protocol Final Version 1.0 date 24-Jul-2025

To determine the	Number	of	falls	Randomisation	to	Participant reported
effect of SAF and	reported	by	а	month 12.		by short forms online,
usual care on the rate	participant	t expre	ssed			by phone or by post
of falls in stroke	as a rate.					each month.
survivors in the 12						
months after						
discharge from						
hospital, compared to						
usual care alone.						

5.1.2 Secondary Endpoint

Table 3: Secondary Endpoints

Table 3: Secondary Endpoints									
Objective	Endpoint Measure	Time Point	Method of Collection						
To determine the effect of SAF and usual care on the number of falls reported by stroke survivors in the 12 months after discharge from hospital and each 3-month period compared to usual care alone.	Number of falls reported by a participant.	Monthly for 12 months Every 3 month period for 12 months (month 1-3, 4-6, 7-9, 10-12)	Participant reported on-line, by phone or by post each month.						
To determine the effect of SAF and usual care on the participant reported severity of falls in stroke survivors in the 12 months after discharge from hospital and each 3-month period compared to usual care alone.	Participant reported severity of falls.	Randomisation to month 12 as well as each 3-month period (month 1-3, 4-6, 7-9, 10-12)	Participant reported by short forms online, by phone or by post each month. Number and type of fall severity (using NDNQI[12] scale).						
To determine the effect of SAF and usual care on stroke survivors' fear of falling compared to usual care alone.	Participant reported fear of falling.	6 and 12 months	Participant Questionnaire – Short Falls Efficacy Scale-International (Short FES-I)[13] (7 questions, resulting in score between 7 and 28).						
To determine the effect of SAF and usual care on stroke survivors' ability to perform instrumental	Participant reported independence.	6 and 12 months	Participant Questionnaire – Extended activities of daily living						

Page 20 of 53

FISS Protocol Final Version 1.0 date 24-Jul-2025

Objective	Endpoint Measure	Time Point	Method of Collection
activities of daily living compared to usual care alone.			(NEADL)[14] (22 questions, resulting in score between 0 and 22).
To determine the effect of SAF and usual care on stroke survivors' and non-professional carers' psychological stress compared to usual	Participant reported psychological stress.	6 and 12 months	Participant Questionnaire – Patient Health Questionnaire (PHQ).[15]
care alone.	Non-professional carer reported psychological stress.	6 and 12 months	Carer Questionnaire- Patient Health Questionnaire Carer (PHQ) to assess psychological distress of non- professional carers.
To determine the effect of SAF and usual care on stroke survivors' quality of life compared to usual care alone.	Participant reported quality of life.	3, 6, 9 and 12 months	Participant Questionnaire – EQ-5D-5L[16] Index/preference scores (minimum value -0.285 and maximum value 1) will be generated from participant responses to the 5 domains. Participant Questionnaire – EQ-5D-5L[16] EQ-VAS (score between 0 and 100).
To determine the cost of implementing SAF and usual care in stroke survivors compared to usual care alone.	Additional treatment and healthcare usage	3, 6, 9 and 12 months	Participant Questionnaire – Health Economics
Process evaluation. To determine whether the SAF	Final interview	< 12 months	Qualitative interviews Number of adaptations made

Page 21 of 53

FISS Protocol Final Version 1.0 date 24-Jul-2025

Objective	Endpoint Measure	Time Point	Method of Collection
programme may influence fall outcomes for who and in what circumstances			Number of falls

5.1.3 Safety Endpoints

The intervention being evaluated is a falls reduction action plan with no expected adverse reactions. The number and severity of falls are collected throughout the study and will be reported as study outcomes. No additional endpoints will be collected for safety.

The severity of each fall will be recorded according to the NDNQI[12] fall severity scale which categorises injurious falls into five levels of severity: None, Minor, Moderate, Major and Death. As this will be collected directly from the participants, "Death" will be removed from the self-report severity scale and where applicable captured separately. For the participant documentation the severity levels will be relabelled as A, B, C, and D, with accompanying descriptions provided to participants instead of the original severity terms.

5.1.4 Stopping rules and discontinuation

There are no planned formal interim analyses. The Sponsor and funder reserve the right to discontinue this study at any time for failure to meet expected recruitment goals, for safety or any other administrative reason. The Sponsor and funder will seek advice from the TSC and DMC before making this decision.

5.2 RANDOMISATION AND BLINDING

5.2.1 Randomisation

Eligible participants will be randomised (1:1) to receive either SAF and usual care or usual care alone. In line with the pragmatic nature of the study, usual care will be determined by local policy and practices.

Treatment allocation will be via a secure, concealed, web-based randomisation service maintained by the Nottingham Clinical Trials Unit (NCTU) hosted on a secure server and accessed via a secure website. Allocation will use a minimisation algorithm including a random component and will minimise on the criteria listed in Table 4 which are all deemed to have potential association with the primary outcome.

Table 4: Minimisation criteria

Table 4. Willingation	Citeria
Stroke service	Minimise imbalances with local factors such as ethnicity and
	deprivation.
Residence	Minimise imbalances related to discharge residence: living
	alone or living with others.
Age	Age of participant is associated with the chance of falling and severity of falls. The following two categories will be used:
	 Aged > 65 years at randomisation
	 Aged ≤ 65 years at randomisation
Baseline MBI score	MBI score is associated with the chance of falling and severity of falls. The following two categories will be used:

Page 22 of 53

FISS Protocol Final Version 1.0 date 24-Jul-2025

Baseline MBI score > 14
Baseline MBI score ≤ 14

